**Part B**

- Overall response rate - i.e. Complete Response (CR) and Partial Response (PR) - of Givinostat at the MTD after 3 cycles; the response will be evaluated according to the clinico-haematological ELN response criteria [21] (see [paragraph 4.6.1](#)).
- Safety and tolerability of Givinostat at the MTD after 3 cycles evaluated as following:
 - Number of patients experiencing adverse events;
 - Type, incidence, and severity of treatment-related adverse events, graded according to CTCAE v. 4.03.

3.2 Secondary endpoints**Part A**

- Overall response rate - i.e. Complete Response (CR) and Partial Response (PR) - of Givinostat at the MTD after 3 and 6 cycles; the response will be evaluated according to the clinico-haematological ELN response criteria [21] (see [paragraph 4.6.1](#)).
- Individual Givinostat concentrations tabulated by dose cohort along with descriptive statistics.

Part B

- Overall response rate - i.e. Complete Response (CR) and Partial Response (PR) - of Givinostat at the MTD after 6 cycles; the response will be evaluated according to the clinico-haematological ELN response criteria [21] (see [paragraph 4.6.1](#)).
- Safety and tolerability of Givinostat at the MTD after 6 cycles evaluated as following:
 - Number of patients experiencing adverse events;
 - Type, incidence, and severity of treatment-related adverse events, graded according to CTCAE v. 4.03.
- Individual Givinostat concentrations tabulated with descriptive statistics.

3.3 Exploratory endpoints**Part A and Part B**

- To evaluate the effect of Givinostat on each single response parameter according to the clinico-haematological ELN response criteria [21] (see [paragraph 4.6.1](#)).
- To evaluate the effects of Givinostat on PD markers by mRNA analysis.

- To evaluate the effects of Givinostat on spleen size (by MRI or CT scan) in patients with confirmed splenomegaly at baseline.
- Improvement of constitutional symptoms evaluated according to MPN-SAF QOL questionnaire [24, 32].
- Reduction of the JAK2^{V617F} allele burden, tested by quantitative RT-PCR.
- Reduction of the symptomatic treatment of pruritus in term of dosage and/or days of treatment.

Part B

- Overall response rate - i.e. Complete Remission and Partial Remission - of Givinostat at the MTD after 6 cycles; the response will be evaluated according to the “**new**” ELN response criteria (i.e. the **revised** ELN response criteria [33], see [paragraph 4.8.7](#)).
- To evaluate the effect of Givinostat on each single response parameter according to the “**new**” ELN response criteria (i.e. the **revised** ELN response criteria [33], see [paragraph 4.8.7](#)).

4. INVESTIGATIONAL PLAN

4.1 Overall study design

This is a two-part, multicenter, open label, non-randomized, phase Ib/II study to assess the safety and tolerability, MTD and preliminary efficacy of Givinostat in patients with JAK2^{V617F} positive PV.

Part A is the dose escalation portion of the study and, once the MTD has been established, **Part B** will commence where the preliminary efficacy of Givinostat in PV patients will be established. Patients will be enrolled either in **Part A** or **Part B** and transition from one part to the other is not allowed. Only PV patients from **Part A** assigned to the dose selected for **Part B** (MTD) may be **counted** towards the efficacy assessment in **Part B**.

Eligible patients for this study will have a confirmed diagnosis of PV according to the revised WHO criteria and the JAK2^{V617F} positivity. Only if the enrolment in **Part A** is slow (i.e. **< 5 patients enrolled in 3 months**), eligibility for this part of the study may be expanded to all patients with cMPN.

After providing informed written consent before undertaking any protocol-related procedure, a unique patient identification code (i.e. **patient screening ID** which will be a combination of his/her site ID, study part ID and patient screening number, e.g. IT01-A01) will be assigned to each patient and it will identify the patient within his/her enrolment confirmation by Italfarmaco S.p.A. or its designee and never be reused in case of screening failure. After the enrolment confirmation and the assignment of the dose level before the first drug intake, a unique patient identification code (i.e. **patient ID** which will be a combination of patient screening number ID and dose level ID, e.g. IT01-A01-DL1) will be assigned to each patient and it will identify the patient

throughout his/her participation in the study and never be reused in case of premature drop-out.

Study therapy will be administered in 28 day cycles. In fact, the “**cycle**” is defined as **4 weeks of treatment**.

Disease response will be evaluated according to the clinico-haematological ELN criteria [21] after 3 and 6 cycles (i.e. at weeks 12 and 24, respectively) of treatment with Givinostat for both parts of the study. All phlebotomies performed in the first 3 weeks of treatment will **not** be counted to assess the clinico-haematological response.

The study will last up to a maximum of 24 weeks of treatment. However, after completion of the trial, all patients achieving clinical benefit will be allowed to continue treatment with Givinostat (at the same dose and schedule) in a long-term study (Study N.: DSC/11/2357/44), provided that the long-term study has already received all necessary approvals in that specific country and site, and the study has been already initiated in that particular site.

Safety will be monitored at each visit throughout the entire duration of the study. Treatment will be administered on an outpatient basis and patients will be followed regularly with physical and laboratory tests, as specified in the protocol (see [Appendix A](#) and [paragraph 4.5.4](#)); in case of hospitalization, the treatment will be continued or interrupted according to the Investigators’ decision.

4.1.1 *Part A*

Part A is the dose escalation part of this study, evaluating the safety, tolerability and MTD of Givinostat in patients with JAK2^{V617F} positive PV.

Approximately 24 patients will be enrolled in *Part A*.

In this part of the study the first cycle of treatment will be used to assess the safety and tolerability of Givinostat as well as PK/PD.

After the completion of the first cycle, the patients will be treated for an additional 5 cycles.

Only PV patients from *Part A* assigned to the dose selected for *Part B* (MTD) may be counted towards the efficacy assessment in *Part B*.

4.1.1.1 Definition of Dose Limiting Toxicity (DLT)

Dose Limiting Toxicity (DLT) is defined as the following **drug-related** toxicity:

- Grade 4 haematological toxicities, **or**
- Grade 3 febrile neutropenia, **or**
- Grade ≥ 3 non-haematological toxicities with exception of:
 - a) Grade 3 diarrhoea without adequate supportive care lasting less than 3 days, **and**

- b) Grade 3 nausea **or** vomiting without adequate supportive care lasting less than 3 days, **or**
- Any drug-related SAE, **or**
 - Any toxicity that is clearly not related to disease progression or intercurrent illness requiring interruption of dosing for more than 3 days during the first cycle.

The severity of the above mentioned events will be graded according to NCI Common Terminology Criteria for AE (CTCAE v. 4.03, 14th June 2010).

Only Dose Limiting Toxicities (DLTs) experienced during the first cycle of treatment will be considered for dose escalation decisions. DLTs include all AEs that are clearly **not** related to disease progression or intercurrent illnesses.

Patients who didn't experience a DLT and missed more than 10% of the doses in Cycle 1 of *Part A* will be replaced (see [paragraph 4.6.4](#)).

4.1.1.2 Study team definition

The study team will include: selected Principal Investigator/s (i.e. Chairman and/or Principal Investigator/s who recruited the patients under discussion), the CRO Medical Monitor, Italfarmaco Medical Expert/s, Italfarmaco Clinical Scientist and any other additional personnel, *if necessary*.

4.1.1.3 Dose Levels (DLs) and dose escalation scheme

Dose escalation will be conducted according to a standard 3+3 design, adopting a modified Fibonacci escalation schema [25, 26, 27]. Patients will be enrolled in cohorts of 3 new patients (up to a maximum of 6) in rising dose levels (Table 1). Dose escalation to the next higher Dose Level (DL) can only occur after the third patient in the DL has been followed for a minimum of 1 cycle after the first administration of study agent, and the current dose has been determined to have an acceptable safety profile according to the following rules summarized in Table 2.

**Table 1 – Dose escalation scheme for Givinostat mono-therapy in Part A**

Givinostat daily dose	Givinostat dose level (DL)	DL used primarily to asses
50 mg b.i.d.	DL0	Safety, PK, PD*
100 mg b.i.d.	DL1	MTD, PK, PD
150 mg b.i.d.	DL2	MTD, PK, PD
200 mg b.i.d.	DL3	MTD, PK, PD
150 mg t.i.d.	DL4	MTD, PK, PD
200 mg t.i.d.	DL5	MTD, PK, PD

* DL previously demonstrated as safe.

The DL0 (i.e. 50 mg b.i.d.) has been previously shown to be well tolerated in studies (Section 6 “Effects in humans” of the current Investigator Brochure Dossier related to ITF2357). Therefore, it is preferred to assign patients to the highest available dose level (i.e. DL1, DL2, DL3, DL4 and DL 5) before assigning patients to DL0.

Intermediate Dose Levels (IDLs) and, consequently, additionally DLs may be introduced to more accurately define the MTD.

Note that if a pregnancy occurs, the patient will be replaced and another patient in that DL should be recruited.

4.1.1.4 Dose escalation rules

In *Part A* each patient will receive study drug at a specific DL. Once the first 3 patients of the first DL (i.e. DL1) have been treated for 1 cycle, tolerability data will be evaluated and a decision to escalate to the next dose will be made.

Table 2 summarizes the dose escalation rules for Givinostat in *Part A*.

Table 2 - Dose escalation rules for *Part A*

Number of patients with DLT at a given dose level	Action
0 out of 3	Enter 3 patients at the next dose level.
1 out of 3	Enter at least 3 more patients at this dose level and 
 if 0 of these 3 new patients experiences DLT, proceed to the next dose level; if ≥ 1 of this group suffer DLT (for a total of $\geq 2/6$ patients with a DLT), this dose exceeds the MTD and dose escalation is stopped. To further assess tolerability, 3 additional patients will be entered at the next lowest dose level if only 3 patients were treated previously at that dose. Upon determination of the MTD, the study proceeds directly to Part B.
≥ 2	Dose escalation will be stopped. This dose exceeds the MTD. To further assess tolerability, 3 additional patients will be entered at the next lowest dose level if only 3 patients were treated previously at that dose and the study will proceed directly to Part B of the study.

At any time, if $\geq 2/3$ or $\geq 2/6$ patients at a given dose level develop a DLT, it is acceptable to de-escalate to an intermediate, not previously studied dose (see Table 1), if evaluation of toxicity at such a dose is desired, in lieu of proceeding directly to *Part B* of the study. If this approach is taken, 3 patients should be enrolled at the intermediate dose, and the aforementioned rules should be used to determine enrolment at this dose. If the decision is made to proceed directly to the efficacy portion of the study (i.e. *Part B*), the efficacy part will start at the next lower dose below where $\geq 2/3$ or $\geq 2/6$ DLTs were observed (i.e. the MTD dose level).

4.1.1.5 Definition of MTD

If 2 or more patients per dose level experience a DLT, dose escalation will terminate and the MTD is the next lower dose level if no more than one out of 6 patients had a DLT at that level. Once all patients enrolled in *Part A* have been treated for at least 1 cycle, the study team will determine the MTD to be used in *Part B* based on the safety and tolerability profile of Givinostat observed as well as the PK and PD data, if applicable.

No intra-patient dose escalation will be permitted prior to determining the MTD.

At that time, patients on treatment at lower dose levels may be allowed to escalate their Givinostat dose up to the MTD for the remainder part of the study (**Part A**) at the discretion of the Investigator **and** after the written authorization of Italfarmaco S.p.A.. Of note, patients initially dosed at lower dose levels that are allowed to escalate their Givinostat dose up to the MTD for the remainder part of the study (**Part A**), will follow the dose modification rules of **Part B** (see [paragraph 4.3.3.2](#)). Total daily dose may never exceed the MTD defined in **Part A** (i.e. 100 mg b.i.d.).

4.1.2 Part B

Part B is a multicenter, open label, non-randomized, phase II, cohort expansion study to assess the preliminary clinical efficacy of Givinostat at the MTD in patients with JAK2^{V617F} positive PV.

Approximately twenty eight patients will be enrolled in **Part B** starting at the MTD defined in **Part A** (i.e. 100 mg b.i.d.), according to an optimized Simon's 2-stage design [30].

The dose of Givinostat will be modified for protocol specified toxicities (see [paragraph 4.3.3.2](#)).

4.2 Trial organization

The conduct of this study will be committed to a Contract Research Organization (CRO). In any case, Italfarmaco S.p.A. remains responsible for the development, writing and finalization of the study protocol, the investigational medicinal product (IMP) production and the Pharmacovigilance activities.

For all study activities, with the exception above mentioned, the designated CRO or their delegates (e.g. a Contract Manufacturing Organization (CMO) delegated for the IMP secondary packaging and management) can apply internal standard operating procedures (SOPs).

Trial activities will be supervised by Italfarmaco S.p.A. through regular contacts with the staff of the designated CRO or their delegates and/or Investigators, *as necessary*.

4.3 Patient population

The study will include patients of both genders with an established diagnosis of JAK2^{V617F} Polycythemia Vera according to the revised WHO criteria, who have an active and/or not controlled disease.

In case of slow recruitment the Sponsor may decide to expand the population to patients with cMPN positive to JAK2^{V617F}.

4.3.1 Inclusion criteria

Patients must meet the following criteria to be eligible for study entry:

1. Patients must be able to provide informed consent through the signature of an informed consent form;
2. Patients must have an age ≥ 18 years;
3. Patients must have a confirmed diagnosis of PV according to the revised WHO criteria;
4. Patients must have JAK2^{V617F} positive disease;
5. Patients must have an **active/not controlled disease** defined as
 - a) HCT $\geq 45\%$ **or** HCT $< 45\%$ in need of phlebotomy, **and**
 - b) PLT counts $> 400 \times 10^9/L$, **and**
 - c) WBC $> 10 \times 10^9/L$;
6. Patients must have an Eastern Cooperative Oncology Group (ECOG) performance status [28] ≤ 1 in **Part A**, ECOG performance status ≤ 2 in **Part B**, within 7 days of initiating study drug;
7. Female patient of childbearing potential has a negative serum or urine pregnancy test within 72 hours of the first dose of study therapy; please note that a borderline urine pregnancy test must be followed with a serum pregnancy test;
8. Use of an **effective** means of contraception for women of childbearing potential and men with partners of childbearing potential;
9. Adequate and acceptable organ function within 7 days of initiating study drug;
10. Willingness and capability to comply with the requirements of the study.

Note that if the enrolment in Part A is slow (i.e. < 5 patients enrolled in 3 months), eligibility for this part of the study may be expanded to all patients with cMPN. In this case, the inclusion criterion n. 5 will be modified as following only for Part A:

5. Patients must have an **active/not controlled disease** defined as:
 - a) ***ET patients:*** PLT counts $> 600 \times 10^9/L$;
 - b) ***MF patients:*** no response according to EUMNET criteria [29].

Note that an **effective** means of contraception for women of childbearing potential and men with partners of childbearing potential (i.e. inclusion criterion n. 5) is defined as following described based on different subject subgroups:

A. Female subjects of childbearing potential: acceptable non-hormonal, contraceptive methods must be used from the 28 days before first dose of study drug through 3 months after the last dose of study drug and include the following:

- True abstinence (absence of any sexual intercourse), when in line with the preferred and usual lifestyle of the subject. Periodic abstinence (e.g. calendar, ovulation, symptothermal, postovulation methods) and withdrawal are not acceptable methods of contraception.

- Double barrier contraception such as diaphragm or a barrier method of contraception in conjunction with spermicidal jelly such as for example cervical cap with spermicide jelly and the male partner must use a condom with spermicide.
- Intra-uterine device (non-hormone-releasing) in place for at least 90 days previously and the male partner must use a condom with spermicide.
- Tubal ligation at least 6 months previously and 1 additional acceptable contraception method.
- Vasectomy of the male partner (with a negative sperm post-vasectomy semen analysis) at least 6 months previously and 1 additional acceptable contraception method.

B. Female subjects of non-childbearing potential must meet at least 1 of the following criteria:

- Postmenopausal: Female subjects, less than 60 years of age, who have been amenorrheic for at least 2 years and have a serum FSH level within the laboratory's reference range for postmenopausal females. Female subject who are 60 years of age or older who are amenorrheic for greater than 2 years will be assume to be postmenopausal.
- Documented hysterectomy or bilateral oophorectomy or both all other female subjects (including subjects with tubal ligations and subjects that do not have a documented hysterectomy) will be considered to be of childbearing potential.

C. Male Subjects, acceptable contraceptive methods must be used from Screening Visit through 3 months after the last dose of study drug, and include the following:

- True abstinence (absence of any sexual intercourse), when in line with the preferred and usual lifestyle of the subject. Periodic abstinence (e.g., calendar, ovulation, symptothermal, postovulation methods) and withdrawal are not acceptable methods of contraception.
- Condom with spermicide and the female partner must use an acceptable method of contraception, such as an oral, transdermal, injectable or implanted steroid-based contraceptive, or a diaphragm or a barrier method of contraception in conjunction with spermicidal jelly such as for example cervical cap with spermicide jelly.
- Vasectomy (with a negative sperm post-vasectomy semen analysis) at least 6 months previously and 1 additional acceptable contraception method.
- Male subjects must not donate sperm from the Screening Visit through 3 months after the last dose of study drug.

Note also that

- Male condom cannot be used with female condom due to risk of tearing.
- The use of birth-control methods does not apply if the female partner has a bilateral oophorectomy, hysterectomy, or is postmenopausal (as defined above).

4.3.2 Exclusion criteria

Patients must **NOT** meet any of the following criteria to be eligible for study entry:

1. Active bacterial or mycotic infection requiring antimicrobial treatment;
2. Pregnancy or nursing;
3. A clinically significant QTc prolongation at baseline (e.g. repeated demonstration of a QTc interval ≥ 450 msec);
4. Use of concomitant medications known to prolong the QT/QTc interval;
5. Clinically significant cardiovascular disease including:
 - a) Uncontrolled hypertension despite medical treatment, myocardial infarction, unstable angina within 6 months from study start;
 - b) New York Heart Association (NYHA) Grade II or greater congestive heart failure;
 - c) History of any cardiac arrhythmia requiring medication (irrespective of its severity);
 - d) A history of additional risk factors for TdP (e.g. heart failure, hypokalemia, family history of Long QT Syndrome);
6. Known positivity for HIV;
7. Known active HBV and/or HCV infection;
8. Platelet count $< 100 \times 10^9/L$ within 14 days before enrolment (i.e. the receipt of the Patient ID);
9. Absolute neutrophil count $< 1.2 \times 10^9/L$ within 14 days before enrolment (i.e. the receipt of the Patient ID);
10. Serum creatinine $> 2 \times$ ULN;
11. Total serum bilirubin $> 1.5 \times$ ULN except in case of Gilbert's disease;
12. Serum aspartate aminotransferase/alanine aminotransferase (AST/ALT) $> 3 \times$ ULN;
13. History of other diseases (including active tumours), metabolic dysfunctions, physical examination findings, or clinical laboratory findings giving reasonable suspicion of a disease or condition that contraindicates use of an investigational drug or that might affect interpretation of the results of the study or render the subject at high risk from treatment complications;
14. Prior treatment with a JAK2 or HDAC inhibitor or participation in an interventional clinical trial for cMPN, including PV, ET or MF;
15. Systemic treatment for cMPN other than aspirin/cardio aspirin;
16. Hydroxyurea within 28 days before enrolment (i.e. the receipt of the Patient ID);
17. Interferon alpha within 14 days before enrolment (i.e. the receipt of the Patient ID);
18. Anagrelide within 7 days before enrolment (i.e. the receipt of the Patient ID);
19. Any other investigational drug or device within 28 days before enrolment (i.e. the receipt of the Patient ID);
20. Patient with known hypersensitivity to the components of study therapy.

Of note, a **repeated** demonstration of a QTc interval ≥ 450 msec (i.e. exclusion criterion n. 3) means that, if the first ECG evaluation demonstrates a prolonged QTc interval (i.e. a QTc interval ≥ 450 msec), two additional ECG evaluations over a brief period of time (i.e. 5 minutes between each recording) must be performed. The averaged value of these three ECG evaluations has to be used for the evaluation of the QTc interval requested by the exclusion criterion n. 3. In the CRF all the performed ECG evaluations have to be entered as well as the average value of multiple ECG evaluation, *if necessary*.

Note that an **any other investigational drug or device** (i.e. exclusion criterion n. 19) includes any investigational drug or device not already mentioned and detailed in the exclusion criteria n. 14, 15, 16 17 and/or 18.

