	
Of note, a repeated demonstration of a QTc interval ≥ 450 msec (i.e. exclusion criterion n. 3) means that, if the first ECG evaluation demonstrates a prolonged QTc interval (i.e. a QTc interval ≥ 450 msec), two additional ECG evaluations over a brief period of time (i.e. 5 minutes between each recording) must be performed. The averaged value of these three ECG evaluations has to be used for the evaluation of the QTc interval requested by the exclusion criterion n. 3. In the CRF all the performed ECG evaluations have to be entered as well as the average value of multiple ECG evaluation, if necessary.
 
Note that an any other investigational drug or device (i.e. exclusion criterion n. 19) includes any investigational drug or device not already mentioned and detailed in the exclusion criteria n. 14, 15, 16 17 and/or 18.

DURATION OF TREATMENT	
The study (both Part A and Part B) will last up to a maximum of 24 weeks of treatment.
 
However, after completion of the trial, all patients achieving clinical benefit will be allowed to continue treatment with Givinostat (at the same dose and schedule) in a long-term study (Study N.: DSC/11/2357/44), provided that the long-term study has already received all necessary approvals in that specific country and site, and the study has been already initiated in that particular site.

CONCOMITANT TREATMENT	
Patients must NOT receive the following treatments during the study:
 
 Other investigational drugs while on this study; Cytotoxic agents, interferons or other approved treatment for cMPN other than aspirin/cardio-aspirin; Any drug known to provoke TdP. 
Other concomitant medications (e.g. symptomatic treatment of pruritus) and significant non-drug therapy (e.g. phlebotomy, blood transfusion) are permitted.

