4.4.5 Concomitant therapy

Patients must **NOT** receive the following treatments during the study:

- Other investigational drugs while on this study;
- Cytotoxic agents, interferons or other approved treatment for cMPN other than aspirin/cardio-aspirin;
- Any drug known to provoke TdP (see [Appendix C](#)).

Other concomitant medications (e.g. symptomatic treatment of pruritus) and significant non-drug therapy (e.g. phlebotomy, blood transfusion) are permitted and must be recorded in the CRF.

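### Exclusion 4 bars QT-prolonging medicines at entry, but the on-study list bars only drugs known to provoke TdP, so a QT-prolonging drug outside that class may be started once Givinostat dosing begins

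*Protocol*

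**What the plan says.** **At entry.** Section 4.3.2 lists conditions that patients must not "meet any of the following criteria to be eligible for study entry". Item 4 is "Use of concomitant medications known to prolong the QT/QTc interval", and the synopsis repeats it. The item cites neither Appendix C nor TdP risk. Items 3, 5c and 5d of the same list also limit QT risk: baseline QTc prolongation, arrhythmia needing medication, and further risk factors for TdP.

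**During treatment.** Section 4.4.5 forbids three groups of treatment:
- "Other investigational drugs while on this study";
- "Cytotoxic agents, interferons or other approved treatment for cMPN other than aspirin/cardio-aspirin";
- drugs known to provoke TdP, with a reference to Appendix C.

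The synopsis gives the third group as "Any drug known to provoke TdP". Section 4.4.5 then allows everything else, beginning "Other concomitant medications (e.g. symptomatic treatment of pruritus) and significant non-drug therapy".

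**Appendix C** is a list of drugs accepted as carrying a risk of TdP. It is not a list of QT-prolonging drugs in general.

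**Withdrawal.** Section 4.3.3.3 requires Givinostat to be stopped, and the patient to leave the study, if a drug on the TdP list is needed. It has no matching rule for other QT-prolonging drugs.

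**The concern.** A medication exclusion on QT grounds protects the patient mainly while the medicine and the study drug are taken together. Here the wider protection applies before the first dose and narrows when exposure starts. The protocol gives no reason for the change.

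New medicines during treatment are foreseeable. Section 1.4 names gastrointestinal toxicities among the most common adverse events. The DLT definition and Table 3 refer to supportive care for diarrhoea, nausea and vomiting. Section 4.4.5 expressly allows symptomatic treatment of pruritus. Treatment lasts up to 24 weeks.

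What is at stake is the safety of a patient who starts such a medicine, and clarity for sites about which rule applies when.

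**Working it through.** The point depends on no formula and there is no stated figure to reproduce. It is a comparison of current version 3.0 text.

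**Step 1: compare the classes.**

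| Rule | Where | Class covered |
|---|---|---|
| Entry | 4.3.2 item 4; synopsis | Medicines known to prolong QT/QTc |
| On-study ban | 4.4.5; synopsis | Drugs known to provoke TdP (Appendix C cited in 4.4.5) |
| Mandatory withdrawal | 4.3.3.3, repeated in the visit sections | Drugs on the TdP list |
| On-study permission | 4.4.5; synopsis | Other concomitant medicines |

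A drug that prolongs QTc without being known to provoke TdP meets row 1, falls outside rows 2 and 3, and is allowed by row 4.

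**Step 2: look for text that carries the wider class into treatment.** Section 6.2.4 defines concomitant medication as what is taken from the first dose onward, but it does so for tabulation and does not govern prescribing. No other current section extends exclusion 4 beyond entry.

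**Step 3: see what Appendix C already removes.** It includes anti-nausea drugs (domperidone, droperidol, chlorpromazine), a gastrointestinal stimulant (cisapride), antihistamines (astemizole, terfenadine) and antibiotics (azithromycin, clarithromycin, erythromycin, moxifloxacin, sparfloxacin). These are barred on study, so the gap is what remains outside the list.

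**Step 4: check whether other safeguards close the gap in Part B.**
- Scheduled on-treatment ECGs: Day 28 of Cycles 1, 2, 4 and 5 (4 recordings) plus Day 28 of Cycles 3 and 6 (2 recordings), so 4 + 2 = 6, with an end-of-study visit as well. A drug started just after one of these visits can go about four weeks without a scheduled ECG.
- A QTc of 450 msec or more leads to two further recordings and an averaged value (4.5.1). No restriction on other medicines follows from it.
- Table 3 acts on a QTc change only if it counts as a Grade 3 or higher non-haematological toxicity or an unmanageable one.
- Extra visits (4.3.3.2.1) follow a toxicity that has already occurred, and their ECG content is not specified.
- The investigator may withhold study drug at any time for safety (4.3.3.3).

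These measures detect or respond to a problem. None bars starting the medicine.

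**The case against.** **Entry rules may properly be stricter than on-study rules.** The two sections govern different periods, so there is no formal contradiction. Exclusion 4 sits beside the baseline QTc criterion, and a clean baseline is a plausible purpose for it. During treatment, banning accepted TdP drugs and requiring withdrawal if one is needed targets the dangerous outcome. This stands as far as it goes: the text can be read as a choice. The protocol does not state that purpose, though, and a clean baseline does not address the period when both drugs are taken together.

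**A reader might infer that the QT class alone was narrowed, and hence that the omission is a plain oversight.** The documents do not support this. Exclusion 19 covers investigational drugs and devices, while 4.4.5 names only drugs. Exclusion 15 covers "Systemic treatment for cMPN other than aspirin/cardio aspirin", while the general term in 4.4.5 is limited to approved treatment. All three groups change in wording between entry and treatment, so no inference about intent can rest on the QT class being singled out.

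**The gap may be small.** Appendix C already covers much of what these patients might be given for nausea, itching or infection, and regular ECG and electrolyte checks exist. This stands, and it limits the severity.

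**The direction of repair is open.** If Appendix C was meant to define both rules, narrowing exclusion 4 would also make the text consistent. That is true. The wider class is preferable because it keeps during exposure the protection that the protocol already requires before it.

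**Conclusion.** The mismatch is real. A QT-prolonging drug not known to provoke TdP excludes a patient at screening and may be started once Givinostat dosing begins. It is a minor, cheaply corrected matter of patient safety and consistency.

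Its size cannot be given. The protocol does not say how many patients might start such a drug, and it does not state how far Givinostat itself prolongs QTc. A reader might infer a known, material cardiac hazard from the gap; the document supplies no basis for that. Nor does the point touch the efficacy results: the two-stage response-rate test, its error rates and the sample size of 28 are unchanged.

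The conclusion assumes that exclusion 4 means what it says, a class wider than Appendix C, and that the on-study list is exhaustive, as its permission for other medicines indicates.

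**What to change.** In 4.4.5 and in the synopsis entry on concomitant treatment, add medications known to prolong the QT/QTc interval to the treatments not to be started on study, using the class named in exclusion 4. Leave mandatory withdrawal under 4.3.3.3 for Appendix C drugs only. State that a patient who needs another QT-prolonging drug is managed under the existing power in 4.3.3.3 to withhold study drug.

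The cost is amendment wording in two places, with no new visits or tests. Sites already apply this class at screening, although the protocol gives no list for it. The downside is that some supportive medicines become restricted during treatment. A patient who needs one may have dosing interrupted, and 4.3.3.3 does not allow a restart after more than 4 weeks of continuous interruption.
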